4.7 Special Consent/Populations

A. Minors-Subjects Who Are Not yet Adults

■ Criteria for Consent of Minors

Minors will not be recruited for the study since they are excluded due to criteria.

■ Wards of the State

Since a ward of the state is either a minor or an incapacitated adult, informed consent directly from the subject cannot be obtained. Therefore they are excluded from the study.

1. Research in NJ Involving Minors

N/A

2. Research Outside of NJ Involving Minors

N/A

■ Parental Permission

Parental permission will not be obtained since minors will not be included in the study. Not applicable to adults.

■ Non-Parental Permission

N/A

- **Affirmation Process**

N/A

- 1. **Documentation of Affirmation**

N/A

- **Non-English Speaking Subjects**

Any prospective subject that meet inclusion criteria will be introduced to the study in their native or preferred language. Common languages in the recruitment area include Spanish but any languages of course can be spoken by the subjects.

- 1. **Process for Non-English Speaking Subjects**

Oral information and discussion will be had with prospective subjects in their native or preferred language through the recruiter using a translator, using a phone system if necessary. Such information will be documented in the consent document.

- **Short Form Consent for Non-English Speakers**

- B. Adults Unable to Consent / Cognitively Impaired Adults (for *interventional studies*)**

- **NJ Law-Assessment of Regaining the Capacity To Consent**

Since the attending anesthesiologist performing the anesthetic in the operating room for the surgery will not be involved in the recruitment, selection, or performance processes in the study, such an attending physician can assess subjects for the ability to consent. As well, the Anesthesia Officer of the Day can also make such a judgment if there is a conflict in determination of ability to consent.

- **Capacity To Consent**

Consent will always be obtained directly and not via surrogates.

- **NJ Law-Selecting A Witness**

There will be no subjects included in this study using a surrogate consent.

For subjects with direct informed consent, the witness to the consent process shall be a Registered Nurse in the area of the consent process not connected to the study, or another physician in the area of the consent process not connected to the study or the surgical case.

- Removing a Subject**

Subjects can be removed from the study immediately any time during or after the intervention or the performance of the supraclavicular nerve block if they express desire to revoke consent or be removed from the study.

4.8 Economic Burden and/or Compensation for Subjects

- A. Expenses**

There is no additional cost to participants undergoing upper extremity surgery, however future patients may benefit from better anesthesia and pain control during the procedure. This study does not address prevention.

- B. Compensation/Incentives**

There will be no provided compensation / incentives for the subjects.

- C. Compensation Documentation**

N/A

4.9 Risks to Subjects

- A. Description of Subject Risk**

There is no additional risk to the subjects since the adequacy of the anesthetic will be assured by an attending anesthesiologist assigned to the surgical case. There is very little risk to the patient even if the onset time of supraclavicular block varies.

B. Procedures for Risks to Embryo, Fetus, and/or Pregnant Subjects

N/A

C. Risks to Non-Subjects

There are no risks to non-subjects.

D. Assessment of Social Behavior Considerations

There is no socio-behavioral risks to the subject using the intervention.

- **Reasonably Foreseeable Risks**

The only reasonably foreseeable risk involving discomfort to the subject would involve an additional non-painful sensation related to nerve stimulation and involuntary muscle contraction in the subjects randomized to nerve blockade with a nerve stimulator.

Risk Of Imposing An Intervention On Subject With Existing Condition

There is no applicable risk to subjects with existing conditions due to the usage of either ultrasound guidance or peripheral nerve stimulator.

- **Other Foreseeable Risks**

There are no other foreseeable risks.

- **Observation And Sensitive Information**

Individuals will not be able to be identified using the information connected. There will be no loss of confidentiality.

E. Minimizing Risks

The intervention will be described to the subject so the subject can anticipate the steps involved in the performance of either ultrasound guided or nerve stimulator guided supraclavicular block. There are no inconveniences to the subject. The risks are very low and already minimized.

F. Certificate of Confidentiality

N/A This is not an NIH study.

G. Potential Benefits to Subjects

Potential benefits to subjects may include faster onset of adequate blockade and anesthesia using supraclavicular nerve block if the intervention would decrease onset time of block.

H. Provisions to Protect the Privacy Interests of Subjects

The privacy interests of subjects will be protected since we will securely store all information related to the subject in the study, and the subject cannot be identified using information collected during the study.

I. Research Team Access to Subject Data

Data relating to the study will be collected using paper tabulation and saved in a locked and secure location / cabinet in the office of the Principal Investigator.

4.10 Secondary Data – Records/Chart Reviews/Databases/Tissue Banks/etc.

N/A

4.11 Chart/Record Review Selection

Since the patient will already have been cleared for the procedure by the surgical and anesthesia team and preoperative testing, the patient will have already been determined to be appropriate for surgery. The attending anesthesiologist for the surgical case and the regional block service anesthesiologist together will have determined that the patient is appropriate for the block before they patient meet inclusion criteria. Therefore EMR's do not need to be reviewed. The patients need to be identified as to inclusion and exclusion criteria by a brief discussion with the patient and the anesthesiologist who evaluated the patient for the surgery.

We will not abstract any data from the medical record since data recording will be done in the holding area or area where the block is performed as block adequacy can be assessed.

4.12 Secondary Specimen Collection

Specimen will not be collected.

- A. N/A
- B. N/A

5.0 Special Considerations

5.1 Health Insurance Portability and Accountability Act (HIPAA)

We will not be obtaining, creating, using, and/or disclosing individually identifiable health information associated with a HIPAA-covered component or entity in the course of the research.

5.2 Family Educational Rights and Privacy Act (FERPA)

Student records will not be accessed.

5.3 NJ Access to Medical Research Act

N/A

5.4 Code of Federal Regulations Title 45 Part 46 (Vulnerable Populations)

These specific populations are excluded from the study.

A. "Special" Classes Of Subjects

- (1) Pregnant Women: see guidance (HRP-412)
- (2) Neonates: see guidance (HRP-413)
- (3) Neonates of Uncertain Viability: see guidance (HRP-414)
- (4) Prisoners: see guidance (HRP-415)
- (5) Children: see guidance (HRP-416)
- (6) Cognitively Impaired Adults: see guidance (HRP-417)

6.0 Research Data Protection and Reporting

6.1 Data Management and Confidentiality

A. Aggregated and de-identified data from paper documentation will be input into an SPSS data file, secured on a password-protected computer kept in the P.I.'s locked office and secured by Rutgers-RWJMS access code. Group data will be analyzed using descriptive statistics, t-tests and ANOVA. Results will be evaluated by the P.I. in consort with the co-investigators to determine whether this clinical trial supports a larger study.

B. *Difference in time of supraventricular block with ultrasound compared to without is 20 and 13 min, respectively with a standard of deviation of 10. This gives an S/N ratio of 0.65. The alpha will be set to 0.05, the power will be set to 0.80. This gives a necessary sample size of 33 for each group. 50 in each group will be sufficient.*

C. **Separation of identifiers will be used for each patient. Data will be stored on a secure cloud.**

D. Data entry will be handled by the PI. 10% of the flow sheets will be reentered by a second clerk, [name], who is a member of the research team and the entries compared for accuracy. If there is more than a 1% difference in data entry, the data will be corrected and the test repeated with another 10 percent of the remaining flow sheets. This process will be repeated until there is a less than 1% disparity between the two data entry processes.

E. All data will be gathered using the same data form (Appendix A). Flow sheets of data will be kept in the P.I.'s locked office. Subjects will be identified by a study number and a copy of the data flow sheet given to the data entry clerk. Data analysis of the confidential data set will be performed by the fellows.

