1.5 Sample Size Justification

For investigation of improved onset time of analgesia, a smaller sample of 34 subjects in each group (N1=34, N2=34) will be sufficient to maintain 80% power and 0.05 alpha level of statistical significance to show 35% decrease in onset time from 20 min to 13 min (effect 0.7) to achieve the Supraclavicular Block with combined use of ultrasound and nerve stimulator.

According to classic studies Williams et al 2003 (doi: 10.1213/01.ANE.0000086730.09173.CA), onset of sensory block parallels onset of partial motor blockade and was 14+/-6 vs 18+/-6 min for ultrasound-guided vs nerve-stimulator guided supraclavicular block.

This was calculated using the power calculation for sample size for continuous outcomes as the dependent variable and two independent samples for the independent variable.

Accrual rates should be about 50% of the available upper extremity renal transplant / vascular graft procedures which should happen at a rate of 2-4 per week.

However, for observation of qualitative data, we decided on a sample size of 100 (N1=50, N2=50).

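### Protocol 6.1B prints a standardised effect of 0.65 where its own inputs give 0.70, and the required total of 64 in 4.5C is below the 66 and 68 that 6.1B and 1.5 imply

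*Protocol*

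**What the plan says.** The protocol gives the minimum sample size for onset time in three places.

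- **Section 6.1B** gives the two means as follows: "Difference in time of supraventricular block with ultrasound compared to without is 20 and 13 min". For the spread and the resulting effect it has: "respectively with a standard of deviation of 10. This gives an S/N ratio of 0.65". With alpha 0.05 and power 0.80 it continues: "This gives a necessary sample size of 33 for each group". It adds that 50 per group will suffice.
- **Section 1.5** states that "a smaller sample of 34 subjects in each group (N1=34, N2=34) will be sufficient to maintain 80% power" at alpha 0.05. The effect assumed there is a "35% decrease in onset time from 20 min to 13 min (effect 0.7"), the shorter time being the one needed "to achieve the Supraclavicular Block with combined use of ultrasound and nerve stimulator". On method it says: "This was calculated using the power calculation for sample size for continuous outcomes as the dependent variable and two independent samples".
- **Section 4.5C** gives the total needed to complete the research as 64, with an aim of 100.

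Two other places bear on the point. Section 6.1A names the analysis: "Group data will be analyzed using descriptive statistics, t-tests and ANOVA". Section 1.6A says that use of the nerve monitor is the only thing that differs between the groups. The target of 50 per group is the same throughout. The SAP adds nothing: its section 8 is template text that asks for the protocol's sample size section to be reproduced.

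**The concern.** Section 6.1B is the only place that gives the SD, so it is the only place where a reader can check the sample size. There the printed effect does not follow from the means and SD in the same sentence, and it contradicts section 1.5. A reader who takes 0.65 as the design effect finds that 33 per group does not reach the stated power.

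The protocol also leaves three different minimum totals for one comparison: 64, 66 and 68. The lowest stands in the section where the required number would be looked up.

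Finally, 6.1B attaches the 20 and 13 minutes to a contrast that this trial does not make, since both groups have ultrasound guidance. It also names the wrong block (supraventricular for supraclavicular).

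**Working it through.** **Inputs.** Means of 20 and 13 min (1.5 and 6.1B), SD 10 min (6.1B), alpha 0.05 and power 0.80 (1.5 and 6.1B), equal groups. The protocol does not state sidedness, so two-sided is assumed and one-sided is tried below.

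**Effect.** d = (20 − 13)/10 = 0.70. To obtain 0.65, the SD would have to be 7/0.65 = 10.77 min, or the difference 0.65 × 10 = 6.5 min. The value 0.65 does equal 13/20, so the ratio of the two means may have been printed. That is an inference; the protocol does not say so.

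**Reproducing the plan's sample sizes.** Normal approximation: n per group = 2(1.960 + 0.842)²/d², computed with unrounded quantiles. The t-test figures come from the noncentral t distribution.

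| Effect | Normal, two-sided | t-test, two-sided | One-sided (normal / t) |
|---|---|---|---|
| 0.70 | 32.04 → 33 | 33.02 → 34 | 25.23 → 26 / 25.94 → 26 |
| 0.65 | 37.15 → 38 | 38.14 → 39 | 29.27 → 30 / 29.97 → 30 |

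The 33 in 6.1B and the 34 in 1.5 are the normal and t-test answers to the same two-sided problem at d = 0.70. Neither is an error. No variant at 0.65 gives 33 or 34, so 0.65 was not the value used. The one-sided results also rule out a one-sided calculation.

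**Totals.** 2 × 33 = 66 and 2 × 34 = 68, against 64 = 2 × 32 in 4.5C.

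**Power.** Normal: Φ(d√(n/2) − 1.960). For example, n = 32 and d = 0.70 give 0.70 × 4 − 1.960 = 0.840, so 79.96%.

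| n per group | d | t-test | Normal |
|---|---|---|---|
| 32 | 0.70 | 78.7% | 79.96% |
| 33 | 0.70 | 79.97% | 81.2% |
| 34 | 0.70 | 81.2% | 82.3% |
| 33 | 0.65 | 73.9% | 75.2% |
| 50 | 0.70 | 93.4% | 93.8% |
| 50 | 0.65 | 89.6% | 90.1% |

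So 64 falls short of 80% by 1.3 points (t-test) or 0.04 points (normal). It is 68 − 64 = 4 patients too few by the t-test, or 66 − 64 = 2 by the normal approximation.

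**Comparison.** Section 1.5 links the fall from 20 to 13 min to combined use of ultrasound and stimulator. Section 1.3 gives both groups ultrasound, and 1.6A leaves the monitor as the only difference. The 20 min can therefore only belong to the ultrasound-alone group, which contradicts the wording in 6.1B.

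**The case against.** The best counter-argument is that nothing in the trial depends on these slips. The target is 100 in every section, and 50 per group gives 89.6% (t-test) or 90.1% (normal) power even at 0.65. The 73.9% figure describes 33 per group, which nobody plans to enrol. This stands, and it is why the point is minor.

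Second, the 64 is a rounding matter: 2 × 32.04, not rounded up. By the normal approximation it misses 80% by 0.04 points, while 33 per group misses by 0.03 points under the t-test. The power shortfall alone is therefore a weak complaint, and 66 is tenable only if the normal approximation is named. The disagreement between the three totals remains.

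Third, the protocol does not define the S/N ratio, so the fault could be a wrong label on a ratio of means. But the sentence says the value follows from figures that include the SD, and a sample size is then derived. Only a standardised difference serves that purpose.

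Fourth, section 1.5 does not say outright that 20 min is the ultrasound-alone mean, and it cites 14 ± 6 min for ultrasound-guided block. The assignment of 20 min follows from the design. Whether 20 min and an SD of 10 are realistic is a separate question, which this correction does not settle.

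**Conclusion.** The concern holds, as a minor correction of stated figures. The 0.65 in section 6.1B is inconsistent with the inputs beside it, with section 1.5, and with the sample size derived from it; those inputs give 0.70. The 64 in section 4.5C is 2 to 4 patients below the totals implied elsewhere and just misses the stated power. The contrast described in 6.1B is not the one under study.

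The conclusion rests on a two-sided 0.05 level, which is the only reading that reproduces the printed sample sizes, and on taking the stated means and SD as given. No patient number or analysis changes.

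**What to change.** - **Section 6.1B:** replace 0.65 with 0.70 and call it the difference divided by the SD. Describe the comparison as ultrasound alone (20 min) against ultrasound plus nerve stimulator (13 min), for supraclavicular block. Replace 33 with 34 per group.
- **Section 4.5C:** replace 64 with 68.
- **Section 1.5:** it already has 34 per group. State there, or in 6.1B, that this is a two-sided t-test at 0.05, which matches the t-tests named in 6.1A.

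Alternatively, use 33 per group (66 in total) in all three places and name the normal approximation.

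If the power of 50 per group is added, give about 93% only as conditional on an effect of 0.70, SD 10, a two-sided t-test and fully observed onset times. Section 1.3B ends the block assessments at 20 minutes, which is the assumed control mean.

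The cost is wording in 6.1B and 4.5C, plus the method statement and, under the alternative, the figure in 1.5. No extra patients are needed, because 100 are already planned.

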6.2 Data Security

As above

6.3 Data and Safety Monitoring

Research does not involve more than minimal risk.

6.4 Reporting Results

A. Sharing of Results with Subjects

No data will be shared with subjects or others.

B. Individual Results

N/A

C. Aggregate Results

N/A

D. Professional Reporting

We plan to publish in reputable articles as well as present at major pain conferences.

E. ClinicalTrials.Gov Registration and Data Reporting

N/A

Notifying participants of their individual results:

Patients will not be notified of their individual results. If patients inquire about the study, they may have access to the collective data for up to 6 years after surgery. The data will be maintained by the P.I. in his office.

Notifying participants of study findings:

Patients will not be notified of the study findings.

Anticipated products or inventions resulting from the study and their use:

None

Disseminating results to public:

We will present the results for review at professional pain and anesthesia meetings, and possibly for journal publication.

6.5 Data Sharing

No sharing of data to other providers.

7.0 Data and/or Specimen Banking

Data will be stored on a secure hard drive with no patient identifiers.

8.0 Other Approvals/Authorizations

School Site Authorization

5.1 Preface

Include a very brief summary (approximately one paragraph) of the important background information from the protocol. This not intended to be used for the design of the study, but rather the significance.

5.2 Scope of the analyses

Include a brief statement of the purpose of the analyses. For example:

These analyses will assess the efficacy and safety of [IMP] in comparison with the [standard] and will be included in the clinical study report.

Provide an example of the Scope.

6 Study Objectives and Endpoints

6.1 Study Objectives

(ICH E3; 8.)

This section describes the overall purpose of the study and is taken directly from the protocol. However, additional elaboration may be helpful.

6.2 Endpoints

(ICH E9; 2.2.2)

List separately the primary, secondary, exploratory endpoints for the study as taken directly from the protocol.

Statistical Analysis Plan: Does the use of nerve stimulator improve the outcome of ultrasound guided supraclavicular block (anesthesia) for upper extremity surgery?

7 Study Methods

7.1 General Study Design and Plan

(ICH E3;9)

Identify the study design, including the following

- Study configuration and experimental design: x-period cross-over, longitudinal, 2x2 factorial, observational, cohort. However, not every design can be abbreviated to a label of few words, and enough detail should always be given to eliminate any ambiguities.
- Type of Comparison: non-inferiority, superiority, equivalence. (ICH E3; 9.2, 9.7.1, 11.4.2.7. ICH E9; 3.3.2)
- Type of control(s): placebo, no treatment, active drug, different dose or administration, historical.
- Level and method of blinding (e.g. double-blind). However, not every method can be abbreviated to a label of few words, and enough detail should always be given to eliminate any ambiguities.
- Method of treatment assignment: Randomization with stratification, minimization.
- At what point in time subjects are randomized relative to treatments, events and study periods.
- Sequence and duration of all study periods: screening, baseline, active treatment, follow-up.

The last two points should routinely be represented by a study flow-chart that can be copied directly from the protocol.

7.2 Inclusion-Exclusion Criteria and General Study Population

(ICH E3;9.3. ICH E9;2.2.1)

This section is intended to describe particulars about all of the subjects in the study. It is distinct from the Analysis Population (section 8.2). This section is intended to describe the intended characteristics of *all* the subjects in the study, whereas the Analysis Population section is designed to identify the characteristics that are needed to defined sub-populations used for the analyses.

The SAP may include:

- a list of all inclusion and exclusion criteria directly copied from the protocol.
- or a simple description of the relevant diagnostic or disease related criteria (e.g. a history of chronic back pain for over 10 years).

Statistical Analysis Plan: Does the use of nerve stimulator improve the outcome of ultrasound guided supraclavicular block (anesthesia) for upper extremity surgery?

7.3 Randomization and Blinding

(ICH E3; 9.4.3, 9.4.6. ICH E9; 2.3.1, 2.3.2)

Describe essential components of the randomization and blinding methodology and process in enough detail to enable its reproduction. Include any minimization, stratification or blocking procedures used to avoid or minimize bias. This section may be copied from the protocol but it may be necessary to include additional information details, particularly regarding block size. However, in a double-blind study it is not appropriate to include such information in the SAP but document it within the final study report, in which case document that these details will be provided in the final study report. Document any software packages used to perform the randomization and the method used for retrieving the treatment assignments.

7.4 Study Assessments

(ICH E3; 9.5.1. ICH E9; 2.2.2)

Describe the frequency and timing of all the relevant assessments. A table or flow chart may be appropriate for example

Visit	Baseline	Month 1	Month 3	Month 6	Month 12
Target day of visit		30	90	180	360
protocol assessment time windows (days)		± 3	± 7	± 14	± 14
History and examination	x	x	x	x	x
Weight	x	x	x	x	x
Vital signs	x			x	x
Hematology	x	x	x	x	x
Biochemistry	x	x	x	x	x
Urinary pregnancy test	x				
Tumor response	x	x	x	x	x
Blood samples for predictive markers	x		x	x	
Concomitant medication	x	x		x	x
Administer treatment		x			
QOL questionnaire	x		x	x	x (12 weeks only)
Adverse event monitoring	x	x	x	x	x

Define the time-windows to be used for converting dates into visit numbers for scheduled assessments (e.g. assessments collected from 27 to 33 days post-Randomization are identified as the Month 1 visit). Describe the decision rules that will be used to classify measurements obtained outside of scheduled protocol specified assessment time-windows. Clearly state how data collected outside the time-windows will be handled for analysis (i.e. how far before and after time-window will data be accepted for use in analysis). Describe the methods for handling multiple measurements

Statistical Analysis Plan: Does the use of nerve stimulator improve the outcome of ultrasound guided supraclavicular block (anesthesia) for upper extremity surgery?

that occur within the same assessment time window. For example, the table below defines the analysis time windows that correspond to the targeted visit time frame.

Analysis Time Windows

Visit (target day)	Lower bound (days)	Upper bound (days)
Baseline (0)	N/A	N/A
Month 1 (30)	2	60
Month 3 (90)	61	135
Month 6 (180)	136	270
Month 12 (360)	271	374

This section will go beyond the description of variables provided in the protocol in that it will list and describe all important study variables from a statistical perspective. The description of each variable should include:

- Identification of any number ranges for numeric endpoints along with their corresponding text descriptors.
 - Items are measured on a 0-100 visual analog scale (VAS) for which 0=no pain and 100=worst pain imaginable
 - Items are measured on a 1-4 ordered categorical scale for which 1=no pain, 2= slight pain, 3=moderate pain, 4=extreme pain

If there are numerous variables it may be useful to create subsections corresponding to each variable which are grouped together as in the protocol (e.g. efficacy, safety) and sections 9-13 of this document.

8 Sample Size

(ICH E3; 9.7.2. ICH E9; 3.5)

This section should reproduce the relevant section from the protocol. If any amendments to the sample size have been made during the study, these should be documented and explained here. If any techniques are used to adjust the primary analysis for sample size adjustment they should be described in the relevant section (10.1).

9 General Analysis Considerations

